7.1.1 Administrative Procedures

7.1.1.1 Informed Consent

The investigator or qualified designee must obtain documented consent from each potential subject prior to participating in a clinical trial.

Consent must be documented by the subject's dated signature or by the subject's legally acceptable representative's dated signature on a consent form along with the dated signature of the person conducting the consent discussion.

A copy of the signed and dated consent form should be given to the subject before participation in the trial.

The initial informed consent form, any subsequent revised written informed consent form, and any written information provided to the subject must receive the institutional review board (IRB) approval in advance of use. The subject or his/her legally acceptable representative should be informed in a timely manner if new information becomes available that may be relevant to the subject's willingness to continue participation in the trial. The communication of this information will be provided and documented via a revised consent form or addendum to the original consent form that captures the subject's dated signature or by the subject's legally acceptable representative's dated signature.

The informed consent will adhere to IRB requirements, applicable laws and regulations, and Sponsor requirements.

7.1.1.2 Inclusion/Exclusion Criteria

All inclusion and exclusion criteria will be reviewed by the investigator or qualified designee to ensure that the subject qualifies for the trial. Written informed consent is required before performing any trial-specific tests or procedures. Signing of the informed consent form can occur outside the 28-day screening period. All screening evaluations must be completed and reviewed to confirm that subjects meet all eligibility criteria before trial entry. Results of standard-of-care tests or examinations performed prior to obtaining informed consent and

within 28 days prior to trial entry (except where otherwise specified) may be used for screening assessments rather than repeating such tests. The investigator will maintain a screening log to record details of all subjects screened and to confirm eligibility or record reasons for screening failure, as applicable.

7.1.1.3 Medical History

A medical history will be obtained by the investigator or qualified designee. Medical history will include all active conditions and any condition diagnosed within the prior 10 years that are considered to be clinically significant by the investigator. Details regarding the disease for which the subject has enrolled in this trial will be recorded separately and not listed as medical history.

7.1.1.4 Prior and Concomitant Medications Review

7.1.1.4.1 Prior Medications

The investigator or qualified designee will review prior medication use, including any protocol-specified washout requirement, and record prior medication taken by the subject within 28 days before starting the trial. Treatment for the disease for which the subject has enrolled in this trial will be recorded separately and not listed as a prior medication.

7.1.1.4.2 Concomitant Medications

The investigator or qualified designee will record medication, if any, taken by the subject during the trial. All medications related to reportable SAEs should be recorded as defined in Section 7.2.

7.1.1.5 Disease Details and Treatments

7.1.1.5.1 Disease Details

The investigator or qualified designee will obtain prior and current details regarding disease status.

7.1.1.5.2 Prior Treatment Details

The investigator or qualified designee will review all prior cancer treatments including systemic treatments, radiation, and surgeries.

7.1.1.5.3 Subsequent Anticancer Therapy Status

The investigator or qualified designee will review all new antineoplastic therapy initiated after the last dose of trial treatment. If a subject initiates a new anticancer therapy within 30 days after the last dose of trial treatment, the 30 day safety follow-up visit must occur before the first dose of the new therapy.

7.1.2 Clinical Procedures/Assessments

7.1.2.1 AE Monitoring

The investigator or qualified designee will assess each subject to evaluate for potential new or worsening AEs as specified in the Trial Flow Chart and more frequently if clinically indicated. AEs will be graded and recorded throughout the trial and during the follow-up period according to the NCI CTCAE v4.03 (see Section 11.1). Toxicities will be characterized in terms of seriousness, causality, toxicity grading, and action taken with regard to the trial treatment.

Please refer to section 7.2 for detailed information regarding the assessment and recording of AEs.

7.1.2.2 Physical Exam

The investigator or qualified designee will perform a complete physical exam at screening/baseline, before every cycle of L-NMMA and pembrolizumab, and at EOT.

7.1.2.3 Vital Signs

The investigator or qualified designee will take vital signs at each physical exam. Vital signs should include temperature, pulse, respiratory rate, and blood pressure. Blood pressure will also be monitored during L-NMMA infusions as described in Section 5.2.1.2 – Dose Modification. Weight will also be measured at each physical exam. Height will be measured at screening only.

7.1.2.4 ECOG Performance Status

ECOG performance status will be assessed at screening/baseline, before every cycle of L-NMMA and pembrolizumab, and at EOT.

7.1.2.5 Electrocardiogram/Multigated Acquisition Scan/Echocardiogram

A 12-lead electrocardiogram will be performed at screening, before every cycle of L-NMMA and pembrolizumab, at EOT, and when clinically indicated. Multigated acquisition (MUGA) scan or echocardiogram (ECHO) will be performed at screening and when clinically indicated. The same method (MUGA scan or ECHO) must be used throughout the duration of the trial.

7.1.2.6 Tumor Imaging and Disease Assessment

Computed tomography (CT) scans of the chest, abdomen, and pelvis and/or other sites as appropriate (e.g., head and neck, upper extremities, lower extremities) will be performed at screening, after every 2 cycles of L-NMMA and pembrolizumab and/or at the discretion of the treating physician and 3 months after the last dose of trial treatment. Disease status will be assessed using the RECIST 1.1.

For subjects with previously treated stable brain metastases, brain CT or magnetic resonance imaging (MRI) will be performed at baseline and every 2 months (± 7 days) as per standard of care.

7.1.2.6.1 RECIST 1.1

The RECIST 1.1 will be used to assess treatment response. Only subjects with measurable disease will be entered into the study. Measurable disease is defined as tumor lesions that can be accurately measured in at least one dimension (longest diameter to be recorded) as ≥ 10 mm on CT, bone metastases with soft tissue masses measuring ≥ 10 mm on CT (CT scan slice thickness no greater than 5 mm), palpable masses measured as ≥ 10 mm with calipers, and clearly delineated lung lesions surrounded by lung parenchyma measured as ≥ 20 mm on chest radiographs. Non-measurable lesions include leptomeningeal disease, ascites, pleural or pericardial effusion, inflammatory breast disease, lymphangitic involvement of the skin or lung, and abdominal masses/abdominal organomegaly identified by physical exam that are not measurable by reproducible imaging techniques. All measurable lesions (up to 5 measurable lesions [2/organ]) representative of all involved organs should be identified as target lesions and recorded and measured at baseline. A sum of the longest diameter for all target lesions will be calculated and reported as the baseline sum longest diameter.

- CR

Disappearance of all target lesions.

- PR

At least a 30% decrease in the sum of the longest diameter of target lesions, using the baseline sum longest diameter as a reference.

- Stable disease (SD)

Neither sufficient shrinkage to qualify for PR nor sufficient increase to qualify for progressive disease (PD), using the smallest sum longest diameter since treatment start as a reference.

- PD

At least a $\geq 20\%$ increase in the sum of the longest dimensions of the target lesions taking as a reference the smallest sum of the longest dimensions recorded since the treatment started, or the appearance of one or more new lesions. In addition to the relative increase of 20%, the sum must also demonstrate an absolute increase of at least 5 mm.

- Clinical PD

Subjects who in the opinion of the treating principal investigator have clinical evidence of PD may be classified as having PD.

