2.2 Secondary Objectives

- To describe the DLTs and other toxicities associated with the L-NMMA and pembrolizumab combination in subjects with melanoma, NSCLC, HNSCC, cHL, urothelial carcinoma, cervical cancer, esophageal cancer, gastric cancer, hepatocellular carcinoma, merkel cell carcinoma, primary mediastinal large B-cell lymphoma, renal cell carcinoma, small cell lung cancer, MSI-H/dMMR cancer, or metastatic tumor mutational burden-high (TMB-H) [≥ 10 mutations/megabase (mut/Mb)] solid tumors, as assessed by the National Cancer Institute Common Terminology Criteria for Adverse Events (NCI CTCAE) v4.03 (see Section 11.1).
- To determine the recommended Phase II dose (RP2D) of the L-NMMA and pembrolizumab combination.
- To evaluate the antitumor activity of the L-NMMA and pembrolizumab combination, as assessed by the Response Evaluation Criteria in Solid Tumors (RECIST) 1.1 (see Sections 7.1.2.6.1 and 11.2).
- To study the plasma pharmacokinetics (PK) and pharmacodynamics of the L-NMMA and pembrolizumab combination.

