3.2 Secondary Endpoints

[figure not shown]
- Secondary endpoints will include evaluation of the A) DLTs and other toxicities (as assessed by the NCI CTCAE v4.03), B) RP2D, C) antitumor activity (as assessed by the RECIST 1.1), and D) plasma PK and pharmacodynamics of the L-NMMA and pembrolizumab combination.

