5.1.2 Subject Inclusion Criteria

Subjects must meet all the following inclusion criteria in order to be eligible for participation in this trial:

- Female or male aged ≥ 18 years on the day of informed consent signing;
- Has histologically confirmed metastatic melanoma that is treatment naïve or has relapsed after or is refractory to ipilimumab or BRAF inhibitor (if *BRAF* mutation positive),
OR
histologically confirmed metastatic NSCLC that has high PD-L1 expression (TPS $\geq 50\%$) with no *EGFR* or *ALK* genomic tumor aberrations or histologically confirmed metastatic NSCLC that is PD-L1 positive (TPS $\geq 1\%$) and has progressed on or after platinum containing therapy (subjects with NSCLC harboring *EGFR/ALK* genomic aberrations must have received an FDA-approved targeted therapy for these aberrations)
OR
histologically confirmed HNSCC that has relapsed after or is refractory to platinum-containing chemotherapy,
OR
histologically confirmed cHL that has relapsed after three or more lines of therapy or is refractory to treatment
OR
histologically confirmed locally advanced or metastatic urothelial carcinoma that is not eligible for platinum-containing chemotherapy or that has relapsed after or is refractory to platinum-containing chemotherapy
OR
histologically confirmed advanced, PD-L1–positive cervical cancer with disease progression on or after chemotherapy that is not eligible for platinum-containing chemotherapy or that has relapsed after or is refractory to platinum-containing chemotherapy
OR
histologically confirmed recurrent, locally advanced or metastatic, squamous cell carcinoma of the esophagus (ESCC) whose tumors express PD-L1 (Combined Positive Score [CPS] ≥ 10), as determined by an FDA-approved test, with disease progression after one or more prior lines of systemic therapy.
OR
histologically confirmed recurrent, locally advanced or metastatic Gastric Cancer , with disease progression on or after two or more systemic therapies, including fluoropyrimidine- and platinum-containing chemotherapy and, if appropriate, HER2/neu-targeted therapy, and whose tumors express programmed death-ligand 1 (PD-L1), as determined by an FDA-approved test.

OR
histologically confirmed hepatocellular carcinoma (HCC) who have been previously treated with sorafenib. recurrent locally advanced or metastatic MCC who had not received prior systemic therapy for their advanced disease. OR

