histologically confirmed recurrent, locally advanced or metastatic Merkel Cell Carcinoma (MCC) who had not received prior systemic therapy for their advanced disease.

OR

histologically confirmed advanced renal cell carcinoma (RCC) first-line treatment.

OR

histologically confirmed metastatic small cell lung cancer (SCLC) with disease progression on or after platinum-based chemotherapy and at least one other prior line of therapy.

OR

histologically confirmed refractory primary mediastinal large B-cell lymphoma (PMBCL), who have relapsed after two or more prior lines of therapy.

OR

MSI-H or dMMR unresectable or metastatic cancer that has relapsed after prior treatment and has no satisfactory alternative treatment options;

OR

adult patients with unresectable or metastatic tumor mutational burden-high (TMB-H) [≥ 10 mutations/megabase (mut/Mb)] solid tumors;

- Measurable disease based on RECIST 1.1;
- Eastern Cooperative Oncology Group (ECOG) performance status of 0–2 (see Section 11.3);
- Life expectancy ≥ 6 months;
- Adequate organ function as defined in Table 4. All screening labs should be performed within 28 days of treatment initiation.

Table 4

System	Laboratory Value
Hematological	
Absolute neutrophil count (ANC)	$\geq 1,500/\text{mm}^3$
Platelets	$\geq 100,000/\text{mm}^3$
Hemoglobin	≥ 9 g/dL (transfusion permitted)
Renal	
Serum creatinine OR Measured or calculated ^a creatinine clearance (CrCl) (glomerular filtration rate can be used in place of creatinine or CrCl)	≤ 1.5 X upper limit of normal (ULN) OR ≥ 60 mL/min for subject with creatinine levels > 1.5 X institutional ULN
Hepatic	
Serum total bilirubin	≤ 1.5 X ULN OR Direct bilirubin \leq ULN for subjects with total bilirubin levels > 1.5 ULN
ALT and AST	≤ 2.5 X ULN OR ≤ 5 X ULN for subjects with liver metastases
Albumin	≥ 2.5 mg/dL
Coagulation	
International normalized ratio (INR) or prothrombin time (PT)	≤ 1.5 X ULN unless subject is receiving anticoagulant therapy as long as PT or PTT is within therapeutic range of intended use of anticoagulants
Activated partial thromboplastin time (aPTT)	≤ 1.5 X ULN unless subject is receiving anticoagulant therapy as long as PT or PTT is within therapeutic range of intended use of anticoagulants

^a CrCl should be calculated per institutional standard.

- Cardiac ejection fraction of $\geq 45\%$;

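### Two lymphomas are eligible, but only a solid-tumor standard is named for their response, and no reporting of response by tumor type is stated

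*Combined protocol and SAP*

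**What the plan says.** Section 5.1.2 admits "histologically confirmed cHL that has relapsed after three or more lines of therapy or is refractory to treatment" and "histologically confirmed refractory primary mediastinal large B-cell lymphoma (PMBCL), who have relapsed after two or more prior lines of therapy". These are two of the 15 disease groups listed in Section 5.1.1. The same section requires, for all subjects, "Measurable disease based on RECIST 1.1".

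The secondary objective on antitumor activity is to be judged "as assessed by the Response Evaluation Criteria in Solid Tumors (RECIST) 1.1" (Section 2.2), so the protocol itself expands the acronym as a solid-tumor standard. Section 3.2 repeats RECIST 1.1 for the matching endpoint, Section 7.1.2.6 applies it to disease status, and Section 7.1.2.6.1 says "The RECIST 1.1 will be used to assess treatment response". Section 11.2 adopts it for the whole study by citing the published guideline, with CT preferred and MRI allowed.

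Section 7.1.2.6.1 then prints its own response categories. All rest on sums of longest diameters. CR requires every target lesion to vanish, PR is a fall of at least 30%, and progression is a rise of at least 20% (and 5 mm) or a new lesion. The investigator may also declare progression on clinical grounds.

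Section 8.0 deals with dose-limiting toxicity, the maximum tolerated dose and the continual reassessment method. It does not mention response.

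**The concern.** Both lymphomas are assessed with an instrument that the protocol labels as one for solid tumors. The protocol makes cHL-specific provision elsewhere: a hematological toxicity rule in Section 5.2.1.2 and sedimentation-rate testing in Sections 6.0, 7.1.3.1 and 7.1.4. The sedimentation rate feeds no response category, and nothing comparable exists for response.

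The printed CR rule fits nodal disease poorly. A lymph node can shrink a great deal and still be visible on CT, and the printed text offers no size at which such a node counts as resolved. The CR rate in lymphoma could therefore be understated.

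In addition, the background response rates differ widely between diseases and no rule says how responses will be summarized. A single undivided figure would be hard to interpret. The stake is the readability of one secondary endpoint.

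**Working it through.** The plan states no target rate, power or interval for response, so there is no figure of its own to reproduce. The check is a comparison of the text, followed by illustrative arithmetic.

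**1. Which criterion applies to lymphoma subjects?**
- Measurability at entry (5.1.2): RECIST 1.1, all diseases.
- Secondary objective and endpoint (2.2, 3.2): RECIST 1.1, not split by disease.
- Disease status and response (7.1.2.6, 7.1.2.6.1): RECIST 1.1, no exception.
- Appendix (11.2): RECIST 1.1, whole study.

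No lymphoma response criterion and no PET imaging appear anywhere in the documents.

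**2. The printed rule applied to a nodal lesion.** Assume one target node, 30 mm at baseline and 9 mm but still visible on treatment, with no new lesions.
- Change in longest diameter = (30 − 9)/30 = 70% decrease.
- This exceeds 30%, so PR is met. The node has not vanished, so CR as printed is not met.

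**3. Effect on the rates.** Assume a denominator of 12, the evaluable number in Section 1.2.1; the documents give no denominator for response. If a lymphoma criterion would call that subject CR and the printed text gives PR:
- CR rate changes by 1/12 = 8.3 points.
- Overall response rate (CR + PR) changes by 0, because the subject is a responder either way.

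**4. Case mix.** Background pembrolizumab response rates in the protocol:
- cHL 65% and 69% (1.1.2.4; CR 16% and 22%)
- Merkel cell 56% (1.1.2.9.2)
- PMBCL 45% (1.1.2.9.5)
- first-line PD-L1-high NSCLC 44.8% (1.1.2.2)
- MSI-H/dMMR 39.6% (1.1.2.6)
- TMB-H 29% (1.1.2.10)
- cervical 14.3% (1.1.2.7)
- gastric 13.3% (1.1.2.9)

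The protocol sets no quota, so take k lymphoma subjects among 12 as an assumption. The expected undivided rate is [k × p(lymphoma) + (12 − k) × p(solid)]/12, with p(solid) from 13.3% to 29%:
- k = 0: 13.3% to 29.0%.
- cHL at 69%, k = 2: (1.38 + 1.33)/12 = 22.6% to (1.38 + 2.90)/12 = 35.7%.
- cHL at 69%, k = 4: (2.76 + 1.064)/12 = 31.9% to (2.76 + 2.32)/12 = 42.3%.
- PMBCL at 45%, k = 2: (0.90 + 1.33)/12 = 18.6% to (0.90 + 2.90)/12 = 31.7%.
- PMBCL at 45%, k = 4: (1.80 + 1.064)/12 = 23.9% to (1.80 + 2.32)/12 = 34.3%.

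The same happens without lymphoma. Two Merkel cell subjects at 56% with ten at 13.3% give (1.12 + 1.33)/12 = 20.4%, against 13.3% for twelve gastric subjects. Reporting therefore needs to be by tumor type, beyond a simple lymphoma/solid split.

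**5. Precision.** The exact 95% interval for 3/12 is 5.5% to 57.2%. Any response rate from this trial is imprecise, whichever criterion is used.

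**The case against.** The strongest reply is that this is a 12-subject dose-finding trial. Response is a secondary endpoint with no hypothesis, and Section 11.2 adopts the full RECIST 1.1 guideline, which may say more about nodes than the summary in Section 7.1.2.6.1. That stands as far as it goes. It limits the consequence, and it rules out saying that a visible node could never be CR, because the documents do not say that the summary overrides the guideline. It does not supply a lymphoma criterion, and it leaves a printed CR rule to be reconciled with its source. Any gap in that rule also affects solid tumors with nodal metastases.

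A reader might infer three stronger things:
- **That lymphoma and solid-tumor responses will be pooled.** No passage says so. Section 3.2 names one endpoint without dividing it, and Section 8.0 specifies no response analysis of any kind.
- **That each lymphoma subject puts 8.3 points of the overall response rate in error.** That figure is one subject's share of any 12-subject proportion. A CR recorded as PR moves the overall rate by zero.
- **That lymphoma alone drives heterogeneity.** Merkel cell carcinoma, at 56%, lies above PMBCL at 45%, and NSCLC at 44.8% is level with it.

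It is also fair to object that no passage mentions a lymphoma criterion usable on CT. The recommendation assumes that the sponsor can identify one.

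**Conclusion.** The point holds in a limited form. The only criterion named for the two lymphomas is a solid-tumor standard. Its printed CR rule puts nodal CR at risk of being recorded as PR, usually with no change in the overall response rate. Neither pooled nor by-tumor reporting of response is stated.

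The documents do not support calling the endpoint mis-measured. The size of the effect cannot be derived, and lymphoma enrolment may be zero. The case-mix figures rest on assumed lymphoma counts, a denominator of 12, and background single-agent rates carried over to the combination. The maximum tolerated dose, the continual reassessment design and the sample size are untouched. This is a low-cost improvement to a secondary endpoint.

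**What to change.** For the antitumor-activity endpoint:
1. Name a lymphoma response criterion for cHL and PMBCL that can be applied to the CT scans already scheduled, and keep RECIST 1.1 for solid tumors.
2. Align the measurable-disease wording in Sections 5.1.2 and 7.1.2.6.1 for these two diseases.
3. Reconcile the CR text in Section 7.1.2.6.1 with the full RECIST 1.1 cited in Section 11.2.
4. State in Section 8.0 that response is listed by tumor type, with lymphoma shown separately from solid tumors.

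Progression also governs whether treatment continues or stops (Sections 5.2, 5.6 and 7.1.4). The sponsor should state which criterion defines progression there for lymphoma subjects and reconcile those sections; no clinical rule is proposed here.

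The cost is wording in Sections 2.2, 3.2, 5.1.2, 7.1.2.6, 7.1.2.6.1, 8.0 and 11.2, plus a response listing that does not yet exist. The drawback is two response instruments in a small trial. If the sponsor does not want that, it could leave the lymphomas out of the response summary and say so in advance. Neither option needs more subjects or a change to dose finding.

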5.2 Trial Treatment

The treatment to be used in this trial is outlined below in Table 5.

Table 5. Trial Treatment

Drug	Dose/Potency	Dose Frequency	Route of Administration	Regimen/Treatment Period
L-NMMA	15.0 mg/kg (starting dose)	Q3W	IV infusion	Days 1–5 of each 3-week cycle
Pembrolizumab	200 mg	Q3W	IV infusion	Day 5 of each 3-week cycle
Q3W = every 3 weeks; IV = intravenous				

L-NMMA and pembrolizumab will be administered for 6 cycles. Cycle length will be 21 days. L-NMMA will be administered as a 2-hour intravenous (IV) infusion on Days 1–5 at each cycle. The dose levels of L-NMMA are as follows: Dose Level -1, 12.5 mg/kg; Dose Level 0 (starting dose), 15.0 mg/kg; and Dose Level 1, 20.0 mg/kg. L-NMMA dose will escalate/de-escalate based on the occurrence of DLTs (see Section 8.0 — Statistical Considerations). Pembrolizumab at a fixed dose of 200 mg will be IV infused over 30 minutes on Day 5 at each cycle. Pembrolizumab will be administered 1 hour (\pm 10 minutes) after L-NMMA infusion on Day 5 at each cycle. Subjects will receive the trial treatment past 3 weeks only if they have tolerated the trial treatment without a DLT and their disease has not progressed. Subjects without disease progression after 6 cycles of L-NMMA and pembrolizumab will continue pembrolizumab until disease progression or unacceptable AEs. Subjects will be followed for a maximum of 3 months after the final treatment dose.

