5.6 Subject Withdrawal/Discontinuation Criteria

Subjects may withdraw consent at any time for any reason or be dropped from the trial at the discretion of the investigator should any untoward effect occur. In addition, a subject may be withdrawn by the investigator or Sponsor if enrollment into the trial is inappropriate, the trial plan is violated, or for administrative and/or other safety reasons. Specific details regarding discontinuation or withdrawal are provided in Section 7.1.4 — Other Procedures.

A subject must be discontinued from the trial for any of the following reasons:

- The subject or legal representative (such as a parent or legal guardian) withdraws consent
- Confirmed radiographic disease progression
- Any AE during Cycle 1 that delays administration of Cycle 2 by more than 7 days or dose interruption that exceeds 21 days in subsequent cycles
- Unacceptable adverse experiences
- Any \geq Grade 4 AE
- Severe (Grade 3) or life-threatening (Grade 4) immune-mediated complication
- Intercurrent illness that prevents further treatment administration
- Investigator's decision to withdraw the subject
- The subject has a confirmed positive serum pregnancy test
- Noncompliance with trial treatment or procedure requirements
- The subject is lost to follow-up
- Death
- Administrative reasons
- Subjects whose blood pressure is >180 during or after L-NMMA infusion and does not return to <160 mmHg after 2 rechecks spaced 15–30 minutes apart

The end of treatment (EOT) and follow-up visit procedures are listed in Section 6.0 (Trial Flow Chart) and 7.1.4.2 (Visit Requirements). At EOT, each subject will be followed for 30 days for AE monitoring (SAEs will be collected for 90 days after EOT as described in Section 7.2.3.1).

Subjects who discontinue for reasons other than progressive disease (PD) will have post-treatment follow-up for disease status until disease progression, initiating a non-study cancer treatment, withdrawing consent, or becoming lost to follow-up.

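### Investigator-opinion Clinical PD sits inside the RECIST 1.1 categories, so the antitumor endpoint can rest on opinion, and a PD label can end disease follow-up

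*Combined protocol and SAP*

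**What the plan says.** Section 2.2 sets antitumor activity as a secondary objective, "as assessed by the Response Evaluation Criteria in Solid Tumors (RECIST) 1.1", and Section 3.2 repeats it as a secondary endpoint: "antitumor activity (as assessed by the RECIST 1.1". Sections 7.1.2.6 and 11.2 name the same criteria. No section says which summary (response rate, disease control, time to progression) will be reported.

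Section 7.1.2.6.1 lists the response categories. PD needs at least a 20% rise over the smallest sum of diameters, or a new lesion. On the rise it adds: "In addition to the relative increase of 20%, the sum must also demonstrate an absolute increase of at least 5 mm". No repeat scan is required. The last entry in the same list is Clinical PD: "Subjects who in the opinion of the treating principal investigator have clinical evidence of PD may be classified as having PD". It states no criteria and requires no scan.

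Section 5.2.3 says the trial is open-label. No central or blinded reading is described.

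Progression also governs treatment and follow-up:
- Section 5.2 allows treatment "past 3 weeks only if they have tolerated the trial treatment without a DLT and their disease has not progressed".
- Section 7.1.4 and Table 6 footnote u continue pembrolizumab until progression, without qualification.
- Section 5.6 lists "Confirmed radiographic disease progression" among the reasons for mandatory discontinuation. No section says what confirms it, when, or by whom.
- Section 5.6 also states: "Subjects who discontinue for reasons other than progressive disease (PD) will have post-treatment follow-up for disease status until disease progression".

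**The concern.** An endpoint described as RECIST 1.1 should follow from lesion measurements and new lesions. Here the investigator's judgement can place a subject in the PD category with no scan, or against the scan, and the protocol does not say that such subjects will be reported apart. A reader of the results could not tell measured progression from judged progression.

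The label also has a consequence of its own. Because Section 5.6 reserves disease-status follow-up for those who stop for reasons other than PD, a subject labelled PD on opinion can drop out of the follow-up that would show whether the lesions progressed.

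The stopping and continuation passages raise a second, smaller matter. One requires confirmed radiographic progression and the others simply say progression, so sites may apply them differently.

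**Working it through.** The plan gives no target, power or rate for the antitumor endpoint, so there is no figure to reproduce. The check sets the passages side by side and adds a scale.

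**1. Two routes to PD in one list.** Take an assumed smallest sum of 50 mm.
- Next scan 60 mm: rise 60 − 50 = 10 mm, 10/50 = 20%. Both thresholds are met, so PD by measurement.
- Next scan 59 mm: rise 9 mm, 9/50 = 18%. Not PD by measurement.
- Now take a baseline of 50 mm, also the smallest sum so far, and a scan at 45 mm with no new lesion: (45 − 50)/50 = −10%. This is short of the 30% decrease for PR and is no increase, so SD. Under the Clinical PD entry the same subject may still be classified as PD.

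Nothing in Sections 2.2, 3.2, 7.1.2.6 or 11.2 says which call enters the endpoint.

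**2. Follow-up after the label.** Section 7.1.2.6.1 says such a subject may be classified as having PD. Section 5.6 gives disease-status follow-up to those who stop for reasons other than PD. Read together, a subject stopped for Clinical PD falls outside it. What remains is the CT that Section 7.1.2.6 schedules 3 months after the last dose.

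**3. The stopping wording.** Section 5.6 requires discontinuation for confirmed radiographic progression. Sections 5.2 and 7.1.4 and footnote u turn on unqualified progression. A site can obey all of them by ceasing treatment once disease has progressed, because the mandatory list in 5.6 does not license further dosing. The gap is that confirmation is undefined and the wording differs.

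**4. Scale.** Section 8.0 gives a maximum of 12 treated subjects.
- One subject moved between SD and PD: 1/12 = 8.3 points of an SD-versus-PD or disease-control proportion. For comparison, the exact 95% interval is 0 to 26.5% at 0/12 and 0.2 to 38.5% at 1/12.
- Section 1.2.1 allows 20 enrolled to reach 12 evaluable. If the denominator were as large as 20, the step would be 1/20 = 5 points.
- The documents give no rate at which opinion and measurement disagree. If each of 12 subjects independently had an assumed probability q of a different call, the chance that at least one differs is 1 − (1 − q)^12: 46% at q = 5%, 72% at 10%, 93% at 20%.

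**5. What does not move.** Clinical PD cannot create a CR or PR. It could lower a response rate only by ending assessment before a response appeared. The DLT definition, the MTD and the dose-finding model in Sections 3.1 and 8.0 do not use progression.

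**The case against.** The strongest defence is that Clinical PD has a job to do. Section 5.2 checks progression for treatment past 3 weeks, but scheduled CT comes "after every 2 cycles of L-NMMA and pembrolizumab and/or at the discretion of the treating physician", so the first is due at 2 × 21 = 42 days. Without an unscheduled scan, clinical judgement is the only way to apply the 3-week check. The endpoint is also secondary and descriptive, in an uncontrolled dose-finding trial. Clinical PD has its own labelled entry, and the CRF is not in the documents, so a separate field may already exist. All of this stands and limits the weight of the point. It does not explain why a judgement used for stopping must also be a RECIST category: Section 5.6 already lists the investigator's decision as a reason to withdraw a subject.

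Several stronger readings are tempting and are not supported:
- A reader might infer three rival definitions of PD for the endpoint. Section 5.6 is a discontinuation rule, not an endpoint definition, and can be obeyed together with 5.2. The conflict that reaches the endpoint lies within 7.1.2.6.1.
- A reader might infer that awaiting confirmation delays the progression date by a full scan interval and adds cycles of L-NMMA. That assumes confirmation only at the next scheduled CT, whereas discretionary scans are allowed, and it assumes dosing that 5.2 would not permit.
- A reader might infer that a PR could be scored after PD. No passage allows it.
- A reader might infer that open-label judgement inflates efficacy, or that toxicity will be scored as progression. Clinical PD tends to lower apparent activity. The text asks for clinical evidence of PD, and adverse events are recorded separately under Section 7.2.

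**Conclusion.** The point holds as a defect in a secondary endpoint. Followed as written, Section 7.1.2.6.1 can give an opinion-based PD in a result labelled RECIST 1.1, and Section 5.6 can then remove the follow-up that would test it. The effect is on SD versus PD as best response, on disease status, and on any progression timing reported. It amounts to 8.3 points per subject for an SD-versus-PD or disease-control proportion with 12 subjects, if such a proportion is reported. A response rate would change little, and the primary endpoint is unaffected.

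The follow-up consequence assumes that PD in Section 5.6 includes Clinical PD. The document does not say otherwise, but a narrower, radiographic-only reading would keep these subjects in follow-up. The undefined confirmation in 5.6 is a separate inconsistency in the stopping text. It bears on the endpoint only indirectly, through time on treatment and who is followed.

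**What to change.** - In Section 7.1.2.6.1, take Clinical PD out of the response categories. Record it in its own CRF field, if there is none already, as a reason for stopping, and list these subjects separately.
- State that RECIST response and PD rest only on lesion measurements or new lesions, and that PD is dated at the first scan that meets the criteria.
- In Section 5.6, keep subjects stopped for clinical PD alone in disease-status follow-up.
- Have the sponsor reconcile the progression wording in Sections 5.2, 5.6 and 7.1.4 and Table 6 footnote u, and define or remove the reference to confirmation. Which standard governs stopping is the sponsor's choice.

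The cost is amendment wording and at most one CRF field. The response rules call for no new types of assessment; the follow-up change extends the disease-status follow-up already in Section 5.6 to the few subjects stopped on clinical grounds alone. The downside is that a few subjects will have no RECIST PD date and must be accounted for in a listing.
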